Each patient enrolled, completing the screening period and meeting eligibility will enter the run-in phase and start with ibrutinib monotherapy pre-treatment on Day -14 through Day -1. While AEs from this period will be collected, they will not constitute part of the DLT evaluation period for combination therapy. The dose for ibrutinib will be 420mg daily, orally.

Cycle 1:

Patients completing the screening period and run-in phase will start the combination treatment. For prevention of IRRs and tumor lysis syndrome the first administration of BI 836826 will be a pre-dose of 10 mg/ml on Day 1. Subsequent two doses will be 50% of the target dose on Day 2 and on Day 8, followed by 100% of the target dose on Day 15 of the first cycle. Patients will continue to receive ibrutinib on days 1-28 of cycle 1. DLTs from the start of the first BI 836826 infusion through the MTD evaluation period (Cycle 1) as well as other AEs will be used to assess dose escalation steps and to determine the MTD.

Cycle 2-4:

Patients will receive 100% of assigned dose of BI 836826 on days 1 and 15 of each cycle. Patients will continue to receive ibrutinib on days 1-28 of each cycle (2-4). At the end of Cycle 3 (Imaging and Laboratory) and Cycle 4 (Laboratory) disease assessment will be performed. Patients without disease progression of CLL will be allowed to continue with BI 836826 and ibrutinib.

Cycle 5-12:

Patients will receive 100% of assigned dose of BI 836826 on Day 1 of each cycle. Patients will continue to receive ibrutinib on days 1-28 of each cycle. Disease assessment will be performed every three cycles or 12 weeks, and will be performed at the end of every third cycle, i.e. Day 21 through Day 28 of Cycle 6, 9, and 12. Treatment with BI 836826 will be terminated at the end of cycle 12 in all patients who achieve PR (MRD positive), PR-L, Stable Disease (SD) or PD in the response assessment at the end of cycle 12. Patients who achieve a CR (MRD positive or negative) or a PR (MRD negative), may continue treatment with BI 836826 as outlined below for additional 12 cycles. Treatment with ibrutinib monotherapy may be continued according to label at the discretion of the investigator or the patient's physician.

Cycle 13-24 (patients with CR and MRD-negative PR only):

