5.3.7 Adverse event collection and reporting

AE Collection:

The following must be collected and documented on the appropriate eCRF by the Investigator:

- From signing the informed consent onwards through REP, until individual patient's end of trial:
 - all AEs (non-serious and serious), and all AESIs.
- After the individual patient's end of trial: the investigator does not need to actively monitor the patient for new AEs but should only report relevant SAEs and relevant AESIs of which the investigator may become aware of.

The REP is defined as 30 days after the last application of BI 836826. All AEs which occurred through the treatment phase and throughout the REP will be considered as on treatment please see [Section 7.3.4](#).

AE reporting to sponsor and timelines

The Investigator must report SAEs, AESIs, and non-serious AEs which are relevant for the reported SAE or AESI, on the BI SAE form via fax immediately (within 24 hours) to the Sponsor's unique entry point (country specific contact details will be provided in the ISF). In specific occasions the Investigator could inform the Sponsor upfront via telephone. This does not replace the requirement to complete and fax the BI SAE form.

Information required:

For each AE, the Investigator should provide the information requested on the appropriate (e)CRF pages and the BI SAE form (if applicable)

The following should also be recorded as an (S)AE in the (e)CRF and SAE form (if applicable):

- Worsening of pre-existing conditions other than the underlying disease
- Changes in vital signs, ECG, physical examination and laboratory test results, if they are judged clinically relevant by the Investigator.

If such abnormalities already pre-exist prior trial inclusion they will be considered as baseline conditions.

All (S)AEs, including those persisting after trial completion must be followed up until they have resolved, have been sufficiently characterized, or no further information can be obtained.

Pregnancy:

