Demographics (sex, birth date, race and ethnicity) will be collected during the screening visit. A detailed cancer history will be obtained. The date of first diagnosis of CLL (month and year may be sufficient) will be recorded in the eCRF. The current stage according to the Rai classification (See [Section 10.1](#)) should be recorded [[R10-4429](#)]. Previously administered chemo- and immunotherapy will be documented, including start and end dates (year and month may be sufficient), the treatment regimen/protocol with the number of courses (chemo-, immunotherapy), the best response obtained (CR, Cri, PR, PR-L, SD, PD, unknown). If the patient has received an autologous Stem Cell Transplant (SCT) or an allogeneic stem cell transplant, procedural details, including the treatment regimen prior to transplantation should be collected. Documentation of previous radiotherapy should include the total radiation dose and radiation field(s). Previous surgeries within the past 5 years should be recorded. In addition, any previous surgery, which may, according to the investigator affect tumor assessment in this trial, e.g. splenectomy or removal of lymph nodes, should be documented in the eCRF.

Re-screening:

Sites will be allowed to re-screen patients. If more than 3 weeks have elapsed prior to re-screening, all screening procedures must be repeated. In case a patient is re-screened, the patient will keep the same assigned patient number.

Below are the specific requirements during the screening period. For a global overview of tests to be performed, please refer to the [Flow Chart](#).

Run-In Phase:

Patients who complete the screening phase and are still eligible will enter the run-in phase. The run-in phase will begin with the first dose of ibrutinib and continue for two weeks of dosing (+/- 2 days) until Cycle 1 Day 1. Patients who are unable to receive $\geq 80\%$ of ibrutinib doses (12 doses) during the run-in phase will be ineligible to continue on trial and would be considered "screen failures". These patients do not need to continue on trial nor complete an EOT Visit or follow-up. They will need to be replaced. To confirm compliance with daily dosing of ibrutinib during the run-in phase and Cycle 1, patients entered in the trial will be required to maintain and complete a dosing diary. At the end of the run-in phase and prior to the first infusion of BI 836826 on day 1, patients must meet the laboratory requirements listed in [Section 4.1.4](#).

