### 6.3 PATIENT SETS ANALYSED

The Screened Set (SCR) includes all patients who signed the informed consent form and will be used to summarize patient disposition.

The Run-In Set (RIS) includes all patients who received at least one dose of ibrutinib. The RIS will be used for the analysis of exposure to ibrutinib.

The Treated Set (TS): consists of all patients who received at least one administration of BI 836826. The TS will be used for all planned safety and efficacy analyses.

The MTD evaluation set: This patient set includes all patients who were documented to have received at least one dose of BI 836826 and were not replaced for the MTD evaluation. The MTD evaluation set will be used for the primary analyses of DLTs and MTD determination.

Rules for replacement of patients are defined in Section 3.3.4.1 of the CTP. The list of replaced patients will be provided by the Trial Clinical Monitor (TCM) no later than the last blinded report planning meeting (BRPM) and will be stored in the TMF.

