## **7.8 SAFETY ANALYSIS**

If not specified otherwise, all safety analyses will be performed on the treated set.

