#### **7.8.1.2 Adverse events**

Unless otherwise specified, adverse events analyses will be performed for the on-treatment period. Selected analyses will be repeated for the MTD evaluation period and for the run-in period.

The analyses of AEs will be descriptive in nature and will follow the standard procedure laid down in (4). All analyses of AEs will be based on the number of patients with AEs and NOT on the number of AEs.

AEs will be coded with the most recent version of MedDRA. The version number will be displayed as a footnote in the respective tables and listings. The severity of AEs will be scaled according to CTCAE version 4.0.

The system organ classes (SOCs) will be sorted alphabetically. In tables displaying AEs by dose cohort, preferred terms (PTs) will be sorted by descending frequency of adverse events in the “Total” BI 836826 group.

Each patient can be observed during the trial under several doses. Analysing the AEs of all treatment courses will be carried out under the initial treatment. No formal statistical analysis is planned for the safety comparison.

The analysis of AEs will be based on the concept of treatment emergent AEs. That means that all AEs occurring from the first administration of BI 836826 until 30 days after last administration of BI 836826 will be assigned to the on-treatment period. All AEs occurring before first administration of any trial medication will be assigned to “Screening”, all AEs occurring after the first administration of ibrutinib and before the first administration of BI 836826 will be assigned to “Run-in” and all AEs occurring after last administration of BI 836826 + 30 days will be assigned to “Post-study” (for listings only). The actual planned dosage of BI 836826 and ibrutinib administered on the day each AE starts will also be derived and will be included in the listing. Listings of screening events will not be sorted by initial treatment. Post-study listings will be sorted by initial treatment. For details on the treatment definition please refer to [Section 6.1](#).

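### The run-in adverse-event tables default to the Treated Set, so patients who took ibrutinib but were removed before BI 836826 are not counted in them

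*SAP*

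**What the plan says.** **The run-in.** Under protocol 4.1.4, eligible patients "start with ibrutinib monotherapy pre-treatment on Day -14 through Day -1". On adverse events in that period the same section says: "While AEs from this period will be collected, they will not constitute part of the DLT evaluation period for combination therapy".

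**The gate.** Protocol 6.2.1 says that patients who cannot receive at least 80% "of ibrutinib doses (12 doses) during the run-in phase will be ineligible to continue on trial". They count as screen failures and are replaced. It adds: "These patients do not need to continue on trial nor complete an EOT Visit or follow-up". The same section also requires patients to meet laboratory criteria at the end of the run-in, before the first BI 836826 infusion.

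**The analysis sets.** SAP 6.3 defines a Run-In Set (at least one ibrutinib dose) and a Treated Set (at least one BI 836826 administration). It assigns the Treated Set to all planned safety and efficacy analyses. For the other set it says only: "The RIS will be used for the analysis of exposure to ibrutinib". SAP 7.8 repeats the default: "If not specified otherwise, all safety analyses will be performed on the treated set".

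**The run-in outputs.** SAP 7.8.1.2 says: "Selected analyses will be repeated for the MTD evaluation period and for the run-in period". It names no patient set. SAP 6.1 and protocol 7.3.4 also call for run-in events to be listed separately, again without naming a set.

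**Follow-up.** Protocol 5.3.7 says: "All (S)AEs, including those persisting after trial completion must be followed up until they have resolved", with adequate characterization or exhausted information as the alternative end points.

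**The concern.** The run-in is the only time in this single-arm trial when patients take ibrutinib alone, so its tables describe how well ibrutinib was tolerated before the antibody was added. Whether a patient reaches the Treated Set depends partly on that tolerability. Protocol 4.1.4.5 cites the label's recommendation to interrupt ibrutinib for certain severe toxicities until recovery, and an interruption that is long enough fails the 80% rule. The patients most likely to be missing from the tables are then those with the events that the tables should show. Protocol 2.3 names increased neutropenia and thrombocytopenia, compared with each single agent, as a potential risk of the combination, so an accurate description of the ibrutinib-only period has some value.

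**Working it through.** **1. The plan's own figure.** Protocol 6.2.1 equates 80% of run-in doses with 12 doses. For a 14-day run-in, 0.80 × 14 = 11.2, which rounds up to 12. The figure reproduces.

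**2. How much interruption fails the gate.** The flow chart and protocol 6.2.1 allow two weeks ± 2 days. With three missed doses:

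| Run-in days | Doses taken | Share | 80% rule |
|---|---|---|---|
| 12 | 9 | 9/12 = 75.0% | fails |
| 13 | 10 | 10/13 = 76.9% | fails |
| 14 | 11 | 11/14 = 78.6% | fails |
| 15 | 12 | 12/15 = 80.0% | passes |
| 16 | 13 | 13/16 = 81% | passes |

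A three-day interruption fails the rule in a run-in of planned length, but not in a 15- or 16-day run-in.

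**3. Where a removed patient falls.** Such a patient has at least one ibrutinib dose and no BI 836826 dose:
- Run-In Set: included.
- Treated Set: excluded.
- Set for the run-in tables: SAP 7.8.1.2 names none, so the default in 7.8 and the assignment in 6.3 apply, which is the Treated Set. Where the SAP wants another set it says so; 7.8.1.1 names the MTD evaluation set for DLTs.

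The patient therefore adds nothing to the numerator or the denominator. The same holds for a patient who fails the end-of-run-in laboratory criteria and never starts BI 836826.

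**4. Size, as an illustration.** The documents give no run-in removal rate. Assume 20 treated patients (the protocol's approximate number), k of them with a given run-in event, and m further patients removed because of that event. The Treated Set shows k/20; the Run-In Set shows (k + m)/(20 + m).

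| k | m | Treated Set | Run-In Set |
|---|---|---|---|
| 0 | 1 | 0/20 = 0% | 1/21 = 4.8% |
| 0 | 2 | 0/20 = 0% | 2/22 = 9.1% |
| 1 | 1 | 1/20 = 5.0% | 2/21 = 9.5% |
| 1 | 2 | 1/20 = 5.0% | 3/22 = 13.6% |

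The direction depends on why patients leave. One removed for a reason without the event, such as loss of ibrutinib supply, adds only to the denominator: 1/20 = 5.0% becomes 1/21 = 4.8%.

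**5. Follow-up.** Protocol 6.2.1 waives the EOT visit and follow-up for these patients, while 5.3.7 requires every (S)AE to be followed. Section 5.3.7 also counts the residual effect period from the last BI 836826 dose, which these patients never had. The text does not say how the two sections fit together.

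**The case against.** Several stronger readings are tempting, and the documents do not support them.

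- *Removed patients vanish from all run-in safety results.* The run-in listings name no set and may include them, and in a trial of about 20 patients listings matter. SAP 6.3 and 7.1.1 also give disposition on the Screened Set, a listing of discontinuations with reasons, and an overview of the analysis sets; ibrutinib exposure uses the Run-In Set. Removals are therefore partly visible. This stands, but a listing does not correct the proportion in a table, and 7.8 read strictly covers listings too.
- *These patients get no follow-up.* The waiver in 6.2.1 can be read as covering scheduled visits only, with 5.3.7 still in force. That is why the two sections need reconciling; it does not show that data are lost.
- *Combination toxicity will be wrongly attributed to BI 836826.* No document makes the run-in a formal comparator, and SAP 7.8.1.2 plans no formal safety comparison. For an informal before-and-after view the Treated Set has a merit: the same patients appear in both periods. Showing the non-starters separately keeps that view.
- *The effect is large.* Nothing supports a high removal rate. Protocol 1.2.2 reports about 5% stopping ibrutinib for adverse events over a median of 8.6 months, and Table 7.1:2 uses 2/51 at 420 mg. Discontinuation is not interruption, but neither figure suggests many removals in two weeks.

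Two further points are fair. Recruitment has stopped and only an abbreviated report is planned, so few patients may be involved. SAP sections 5.4.2 and 5.4.5 are cited but absent from the public text, so a run-in specification there cannot be ruled out; the visible 6.3 and 7.8 point to the Treated Set.

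**Conclusion.** The point holds for the run-in adverse-event tables. As written, they count only patients who went on to BI 836826, so they leave out patients removed during the run-in, including any removed for toxicity. Ibrutinib-alone toxicity can then be understated. This rests on the SAP default applying wherever no other set is named.

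The size cannot be stated. The illustration (0% against 4.8% or 9.1%) assumes 20 treated patients, no event among them, and one or two removals, all for the event in question. If nobody was removed, the tables are the same on either set.

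The number of patients with DLTs and the MTD are unaffected, because run-in events are outside the DLT evaluation. This is a correction worth making before the report outputs are produced; it does not threaten the primary result.

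**What to change.** 1. In SAP 6.3 and 7.8.1.2, state that the run-in adverse-event tables and listings use the Run-In Set, with patients who did not start BI 836826 in a separate row or column.
2. In SAP 7.1.1, show run-in failures with their reasons in the disposition table, apart from patients who failed screening before any ibrutinib.
3. Reconcile protocol 6.2.1 with 5.3.7 for patients whose adverse events began after the first ibrutinib dose, so that it is clear what the waiver covers and when collection ends for someone without a BI 836826 dose.

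The cost is small. The Run-In Set is already defined, adverse events are already collected from consent, and items 1 and 2 need a few sentences and an extra row or column. They can be applied to data already collected although recruitment has stopped.

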### **7.8.1 Adverse events**

#### **7.8.1.1 Maximum tolerated dose / RP2D and dose limiting toxicity**

A summary of the number of patients with DLTs within the MTD evaluation period will be displayed for the MTD evaluation set. This table will also be created for all treatment courses of the on-treatment period by initial treatment for the treated set.

Patients who were replaced within the MTD evaluation period will be excluded from the determination of the MTD but will be considered for all other safety evaluations. A listing of replaced patients will be provided.

Refer to [Section 7.4](#) for more details on the analysis of the MTD and the RP2D.

#### **7.8.1.2 Adverse events**

Unless otherwise specified, adverse events analyses will be performed for the on-treatment period. Selected analyses will be repeated for the MTD evaluation period and for the run-in period.

The analyses of AEs will be descriptive in nature and will follow the standard procedure laid down in (4). All analyses of AEs will be based on the number of patients with AEs and NOT on the number of AEs.

AEs will be coded with the most recent version of MedDRA. The version number will be displayed as a footnote in the respective tables and listings. The severity of AEs will be scaled according to CTCAE version 4.0.

The system organ classes (SOCs) will be sorted alphabetically. In tables displaying AEs by dose cohort, preferred terms (PTs) will be sorted by descending frequency of adverse events in the “Total” BI 836826 group.

Each patient can be observed during the trial under several doses. Analysing the AEs of all treatment courses will be carried out under the initial treatment. No formal statistical analysis is planned for the safety comparison.

The analysis of AEs will be based on the concept of treatment emergent AEs. That means that all AEs occurring from the first administration of BI 836826 until 30 days after last administration of BI 836826 will be assigned to the on-treatment period. All AEs occurring before first administration of any trial medication will be assigned to “Screening”, all AEs occurring after the first administration of ibrutinib and before the first administration of BI 836826 will be assigned to “Run-in” and all AEs occurring after last administration of BI 836826 + 30 days will be assigned to “Post-study” (for listings only). The actual planned dosage of BI 836826 and ibrutinib administered on the day each AE starts will also be derived and will be included in the listing. Listings of screening events will not be sorted by initial treatment. Post-study listings will be sorted by initial treatment. For details on the treatment definition please refer to [Section 6.1](#).

According to the BI standards, multiple recordings of AEs will be collapsed to episodes on the lowest level term and multiple episodes will be condensed to records on the PT and SOC level. CTCAE grade will be an additional criterion for collapsing and condensing AEs. The maximum CTCAE grade will be assigned to episodes and records. CTCAE grade and DLT information will be displayed in AE listings. MedDRA levels for condensing will be SOC and PT.

An overall summary of adverse events will be presented.

#### Reporting of CTCAE grades:

CTCAE grading within AE tables in Section 15 of the CTR is displayed as “all Grades”, “missing Grade”, “Grade 1”, “Grade 2”, “Grade 3”, “Grade 4” and “Grade 5”, but the “missing grade” column should only be displayed in case AEs with a missing CTCAE grade occurred. A separate table will show AEs leading to death. In this table no CTCAE grades will be shown.

Frequencies of patients with AEs will be summarised by treatment, highest CTCAE grade, primary SOC and PT. Tables will be provided for patients with drug-related AEs, with serious AEs (SAEs), with drug-related SAEs, with AEs leading to discontinuation of last study medication (i.e. leading to discontinuation of the last administered study medication), with AEs leading to discontinuation of BI 836826, with AEs leading to discontinuation of ibrutinib, with AEs leading to dose reduction of BI 836826, with AEs leading to dose reduction of inbrutinib, with protocol-specified AEs of special interest (AESI), and with AEs leading to death.

## **7.8.2 Laboratory data**

The analyses of laboratory data will be descriptive in nature and will follow the standard procedure laid down in (2). Patients will be counted under the initial treatment. The analysis of laboratory data will use the same ‘analysing treatments’ as described for the AEs, except for that the baseline laboratory value (as defined in [Section 6.7](#)) will be included in the ‘on treatment’ period. Patients having at least one post-baseline laboratory value will be displayed in the descriptive analyses. Patients with missing CTCAE grade at baseline or no baseline value but with post-baseline laboratory values will be displayed in the category “Missing CTCAE grade at baseline”.

Single time courses by initial treatment will be used to display normalized laboratory values over time by dose cohort. The graphs may be truncated if sufficient data is not available. These graphs will be displayed in Section 16.1.13.1 of the CTR for the following parameters, using the BI normalised values for haematology and differentials, and the multiples of the ULN for enzymes.

Haematology: haemoglobin, white blood cell count

Differentials: absolute lymphocyte count

Enzymes: LDH

Descriptive statistics, including change from baseline, frequency of patients with transitions relative to the references range, will be provided. No post-study laboratory values will be considered. CTCAE grade for applicable laboratory parameters will be calculated according to CTCAE v4.0. The following outputs will be presented:

- Worst CTCAE grade experienced during the on-treatment period
- Transitions of the CTCAE grade from baseline to the worst lab values, from baseline to the last lab values, and from the worst to last values during the on-treatment period
- Possible clinically significant laboratory values

Note: For calculating the change in CTCAE grade from baseline, patients with a CTCAE grade of -9 (no CTCAE grade defined) will be treated as a CTCAE grade 0 for all analyses. In laboratory listings, the CTCAE grade is displayed as -9.

For Uric Acid and Hypokalemia, the CTCAE grade cannot always be assigned by the laboratory parameter itself as two different CTCAE grades have the same laboratory constellation, but are distinguished by additional clinical parameter. In this case a CTCAE grade of -1 will be assigned initially. Patients with a CTCAE grade of -1 will be treated as

- Grade 1 for Uric Acid
- Grade 1 for Hypokalemia

for all analyses. In laboratory listings, the CTCAE grade will be displayed as -1.

The prioritized laboratory values (see [Section 5.4.5](#)) will be displayed in Section 15 of the final CTR while all other laboratory parameters will be displayed in the Appendix of the CTR.

Patients with hepatic enzyme elevation will be tabulated (drug-induced liver injury (DILI) supporting table). In addition, a separate listing will be presented giving patients with missing parameter in the given time frame.

For potential Hy's law cases, possible clinically significant abnormal laboratory values and cases of TLS frequency tables will be provided.

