3.3.2 Inclusion criteria

1. Diagnosis of CLL established according to IWCLL criteria ([R10-4429](#)) and documented within medical records.
2. Relapsed or refractory CLL pre-treated with at least one prior line of systemic therapy for CLL.
3. Indication for treatment consistent with IWCLL criteria, i.e. at least one of the following criteria should be met
 - a) Evidence of progressive marrow failure as manifested by the development of, or worsening of, anaemia and/or thrombocytopenia.

- b) Massive (i.e., lower edge of spleen ≥ 6 cm below the left costal margin) or progressive or symptomatic splenomegaly.
 - c) Massive nodes (i.e., ≥ 10 cm in longest diameter) or progressive or symptomatic lymphadenopathy.
 - d) Progressive lymphocytosis in the absence of infection, with an increase in blood ALC $\geq 50\%$ over a 2-month period, or a lymphocyte doubling time (LDT) of < 6 months (as long as initial ALC was $\geq 30000/\mu\text{L}$).
 - e) Autoimmune anaemia and/or thrombocytopenia that is poorly responsive to corticosteroids or other standard therapy.
 - f) Constitutional symptoms, defined as any one or more of the following disease-related symptoms or signs:
 - i. unintentional weight loss of 10% or more within the previous 6 months
 - ii. significant fatigue (i.e. ECOG PS 2 or worse; inability to work or perform usual activities)
 - iii. fevers higher than 100.5°F or 38.0°C for ≥ 2 weeks without other evidence of infection
 - iv. night sweats for > 1 month without evidence of infection
4. Clinically quantifiable disease burden defined as at least one of the following:
- a) either ALC $> 10\,000/\mu\text{L}$, or
 - b) measurable lymphadenopathy (at least one node > 1.5 cm in short diameter on CT or Magnetic Resonance Imaging (MRI) or
 - c) quantifiable bone marrow infiltration documented in a bone marrow biopsy during screening
5. Minimum interval to prior CLL treatment in line with the following requirements:
- a) Last dose of a cytotoxic drug, a monoclonal antibody targeting CD20, or an investigational drug to treat CLL at least 1 week prior to the first dose of ibrutinib.
 - b) Last dose of idelalisib at least 48 hours prior to the first dose of ibrutinib.
 - c) Last dose of alemtuzumab at least 4 weeks prior to the first dose of ibrutinib.

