## 6. GENERAL ANALYSIS DEFINITIONS

### 6.1 TREATMENTS

In this trial, treatments are not randomized (open-label, dose-escalation). Different dose levels of BI 836826 in combination with ibrutinib are being administered. All planned analyses will be presented by initial treatment group, i.e. for all dose cohorts separately and in total over all dose cohorts.

To justify the RP2D / MTD determination, DLTs occurring during the MTD evaluation period will be presented separately from those occurring during the whole on-treatment period. Patients where treatment group assignment has not been followed will be handled on a case-by-case basis and will be agreed upon latest at the report planning meeting before database lock.

For safety summaries events that start from first administration of BI 836826 and last until 30 days (residual effect period (REP)) after the last administration of BI 836826 will be considered as having occurred “on treatment”. If not specified otherwise, all safety tables will be based on the on-treatment period. AEs that have an onset date during the screening, run-in, or post-study period will be displayed in separate listings from those occurred during the on-treatment period (refer to [Section 7.8.1.2](#) for details).

Labels of each analysis treatment period, analysis numbers, the labels used for displays in the tables and listings in the CTR, as well as codes, decodes, sort order and labels for each trial medication are provided in the TSAP technical document analysis dataset (ADS) plan.

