## **6.7 BASELINE, TIME WINDOWS AND CALCULATED VISITS**

Study days and visits will be labelled according to the flow chart of the CTP.

Unless otherwise specified, baseline is defined as the time-point closest to but prior to first administration of BI 836826. If no time is specified and the date is the same as the first administration date, then it will still be considered baseline if not specified otherwise.

Laboratory values: Baseline is defined as the latest time-point before the very first administration of BI 836826. For laboratories where not only the examination date but also time are recorded, examination time has to be taken into account when defining baseline. That is, a laboratory value on the same date as the first administration of BI 836826 is considered as baseline value if and only if the time of laboratory value is before or the same as the time of BI 836826 administration.

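### SAP 7.8.2 lets the pre-dose baseline laboratory value count as the worst on-treatment CTCAE grade, which overstates the grade for patients whose every later grade is better

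*SAP*

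**What the plan says.** SAP 6.1 sets the on-treatment period for safety summaries as "events that start from first administration of BI 836826 and last until 30 days (residual effect period (REP)) after the last administration of BI 836826". SAP 7.8.1.2 follows this for adverse events and assigns those that occur between the first ibrutinib dose and the first BI 836826 dose to a separate run-in period.

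SAP 7.8.2 takes over these periods for laboratory data, "except for that the baseline laboratory value (as defined in [Section 6.7](#)) will be included in the" on-treatment period. The baseline meant is the one in SAP 6.7: "Baseline is defined as the latest time-point before the very first administration of BI 836826".

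The outputs in SAP 7.8.2 then include:
- "Worst CTCAE grade experienced during the on-treatment period";
- three grade-shift comparisons: baseline against worst, baseline against last, and worst against last;
- possible clinically significant values, which Protocol 7.3.4 defines in general as at least grade 2 with a rise in grade from baseline.

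SAP 7.8.2 also states: "Patients having at least one post-baseline laboratory value will be displayed in the descriptive analyses".

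**The concern.** A value taken before any BI 836826 is placed in the on-treatment period, and the worst grade is then read from that period. Nothing in the SAP text restricts the worst grade to later samples.

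Abnormal baselines are realistic in this population. One listed indication for treatment is "Evidence of progressive marrow failure as manifested by the development of, or worsening of, anaemia and/or thrombocytopenia". Table 3.3.2:1 admits patients with haemoglobin from 8 g/dL, neutrophils from 1000/µL and platelets from 25000/µL. The laboratory baseline also follows about two weeks of ibrutinib.

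The plan also expects some of these counts to recover. Protocol 5.1.1 names improvement of low baseline counts among the efficacy criteria for the RP2D, and Appendix 10.2 lets a 50% improvement in platelets, haemoglobin or neutrophils support a partial response. A patient who recovers in this way is the one the rule misreports.

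Neutropenia and thrombocytopenia are the combination risks named in Protocol 2.3, so the worst-grade table is one that readers of the abbreviated report will look at.

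**Working it through.** The plan gives no figure to reproduce; the check is on the definition.

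**Inputs.** Let b be the baseline grade (SAP 6.7) and m the worst grade among samples after the first BI 836826 dose. Both run from 0 to 4.

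**Two definitions of worst on-treatment grade.**
- SAP 7.8.2 as written: W = max(b, m).
- Post-baseline samples only: W = m.

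**Where they differ.** max(b, m) differs from m only when b > m. Of the 5 × 5 = 25 combinations, 4 + 3 + 2 + 1 = 10 satisfy this. These are combinations, not probabilities. In all 10 the SAP value is the higher, so the error is never downward. A cytopenia that persists at the same grade is counted under either definition.

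| Patient | b | m | As written | Post-baseline only |
|---|---|---|---|---|
| Improves | 3 | 1 | 3 | 1 |
| Persists | 3 | 3 | 3 | 3 |
| Worsens | 1 | 3 | 3 | 3 |

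**Baseline-to-worst.** Since max(b, m) ≥ b, no cell below the diagonal can be filled. The first two patients both appear as 3 to 3.

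**Worsening.** max(b, m) > b holds exactly when m > b, so the set of patients counted as worsened is the same under both definitions. Possible clinically significant values require a rise in grade, so they do not change either.

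**Worst-to-last.** For the improving patient the table starts at the pre-dose grade 3 and shows recovery from an abnormality that preceded BI 836826.

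**Baseline-to-last.** This is unaffected. A displayed patient has a post-baseline value, so the last value is post-baseline, provided the display rule is applied to each parameter separately.

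**Size.** One affected patient moves a grade row by 1/3 = 33 percentage points in a cohort of three, or 1/20 = 5 points in all 20 planned patients. Let q be the share of patients with baseline grade 3 or more and only lower grades later. The documents give no q, so the values below are assumptions. Expected number added to the grade 3 or more rows = 20q; chance of at least one = 1 − (1 − q)^20.

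| Assumed q | Expected patients added | Chance of at least one |
|---|---|---|
| 5% | 1 | 64% |
| 10% | 2 | 88% |
| 20% | 4 | 99% |

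**The case against.** The strongest reply is that the SAP may only be filing the baseline value with the on-treatment data so that change and transition tables have a reference. The transitions treat baseline and worst as separate things. Laboratory analyses also follow a sponsor standard (SAP reference 2) that is not available here, and SAP 7.8.2 points to a Section 5.4.5 that is not in the public text. Either could define worst as post-baseline. This is possible, but the SAP text that can be read says the opposite, and the requirement for a post-baseline value selects patients, not the values that enter the maximum.

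The second reply concerns frequency, and it stands. Protocol 1.2.1 and 2.3 report that neutrophils and platelets fall immediately after infusion. The Flow Chart schedules blood counts on Cycle 1 Days 2, 8, 15 and about 20, and its footnote 15 adds a safety sample 1 to 3 hours after the first infusion. Many patients will have a post-dose value at least as bad as baseline. For neutrophils, the entry threshold of 1000/µL matches the point that Protocol 4.1.4.5 treats as grade 2 or better, so grade 3 or 4 is excluded at screening, although ibrutinib follows before baseline.

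The third reply also stands: other outputs limit the damage. Baseline-to-last transitions and change from baseline show improvement directly.

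A reader might infer that these tables attribute disease-related or run-in cytopenia to BI 836826. They do not. A worst-grade table carries no causality assessment, and relatedness is reported through the drug-related adverse event tables. What is misstated is timing.

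**Conclusion.** The rule is wrong as written. It reports a pre-dose grade as worst on treatment for any patient whose baseline grade exceeds every later grade, hides improvement in the baseline-to-worst table, and can start worst-to-last from a pre-dose value. The error is upward only. Its size depends on a share of patients that the documents do not give; the 5% to 20% range above is illustrative.

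It would be tempting to conclude that the dose decision is affected. The documents do not support that. DLT counts, the BLRM, the MTD and the adverse event tables do not use this rule. Protocol 5.1.1 allows laboratory abnormalities to be considered for the RP2D but does not refer to this table. The analyses are descriptive, development has been discontinued, and only an abbreviated report is planned.

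Severity is moderate to low. The conclusion assumes that no text outside the available SAP restricts worst to post-baseline values.

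**What to change.** In SAP 7.8.2, keep the baseline value as the reference for change from baseline and for the transition tables. State that the worst on-treatment value is derived only from samples taken after the first BI 836826 administration, up to the last administration plus 30 days. Use the timing rule in SAP 6.7 to separate baseline from post-baseline samples on the first dosing day. If the sponsor's laboratory standard already restricts worst in this way, say so in 7.8.2 and remove the conflict with the current sentence.

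The cost is one sentence and one dataset flag. No new data are needed, and the baseline grade can still be displayed.
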